To minimize these adverse events, the American Academy of Pediatrics and the International Neuropsychiatric Pain Group recommend reducing pain in infants and using non-pharmacological pain relief methods as the primary option in newborns (18, 19). Studies indicate that non-pharmacological tactile stimuli such as vibration may have the potential to reduce pain due to the presence of numerous large fibers in the skin (11, 20-22). Infants are exposed to mechanical vibration through vibrating infant seats or swings to calm them in both hospital and home settings (23). However, it is known that vibration applied with a mechanical hand vibrator is also used as a method of chest physiotherapy in Neonatal Intensive Care Units (NICUs) to calm colicky infants (24, 25).

It has been suggested that manipulations such as rubbing, applying pressure, and tapping directly on or below painful areas may also alleviate pain by releasing beta-endorphins into the bloodstream (13). It has been suggested that simple manual pressure applied to the injection site (similar in effect to the fiske method) may be a useful technique for reducing injection pain (7, 13, 26). The current literature shows that non-pharmacological mechanical vibration and fiske applications may be effective in reducing injection pain (7, 11).

Based on this information, the aim is to evaluate the effect of mechanical vibration and fiske tapping methods in reducing pain during vaccination in one-month-old infants receiving healthcare as part of routine primary preventive healthcare services.

Aim

This study aims to investigate the effect of tapping the injection site prior to the second dose of Hepatitis B vaccine administered to the anterior surface of the vastus lateralis muscle during infancy and the application of mechanical vibration to the injection site throughout the vaccination procedure on acute pain, crying duration, and physiological parameters that may occur due to intramuscular injection.

Research Hypotheses

Main Hypotheses

Hypothesis 0a (H0a): There is no difference in pain between the control group and the study groups when mechanical vibration is applied during Hepatitis B vaccination in infants compared to routine Hepatitis B vaccination.

Hypothesis 1a (H1a): There is a difference in pain between the control group and the study groups when mechanical vibration is applied during Hepatitis B vaccination in infants compared to routine Hepatitis B vaccination.

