A power analysis was performed to select the patients to be sampled. The G*Power 3.1.9 program was used to calculate the number of participants to be included in the study. During the calculation, the effect size was taken as 0.31 based on Kanbur's (2021) study for the parameters specified according to the type of test, the margin of error was taken as 0.05, the power value was taken as 0.80, the number of groups was taken as 3, and the number of measurements was taken as 3. The calculation resulted in a minimum participant number of 72. Accordingly, it was planned to include a minimum of 24 participants in each group (27).

Research Inclusion Criteria

The parent agrees to participate in the study/volunteers to participate,

The gestational age is between 38 and 42 weeks,

The birth weight is between 2500 g and 4000 g,

No pain medication is administered prior to vaccination,

Body temperature is within normal limits,

Exclusion Criteria

Parents who do not consent to participate in the study,

Gestational age below 38 weeks or above 42 weeks,

Infants with congenital diseases or birth defects will not be included in the study.

Data Collection Tools

Newborn Baby Identification Form

The newborn infant information form created by the researcher consists of a total of nine questions, including the infant's group number, gender, gestational age, mode of delivery, birth weight and length at birth, postnatal age, current weight and height, and feeding method (27, 29).

Parent Information Form

The parent information form created by the researcher consists of a total of six questions, including the parent's group number, mother and father's ages, education status, and occupation information (27).

Newborn Baby Observation Form

The observation form prepared by the researcher is a form on which physiological parameters will be recorded, including the baby's group, crying time with the start of the vaccination procedure, the baby's body temperature before and after the procedure, the baby's respiratory rate before and after the procedure, and oxygen saturation and heart rate before, during, and after the procedure. This information about the infant before, during, and after the procedure **will be observed by the researcher and recorded on this form (27, 29).**

Neonatal Infant Pain Scale (NIPS)

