IBM SPSS 27 software will be used to analyze the data in this study. Continuous data will be presented as mean \pm standard deviation, while categorical data will be presented as frequency and percentage. If the values obtained from the measurements taken for each variable throughout the study show a normal distribution, the parametric test ANOVA test will be used to compare repeated measurement results. If the values do not show a normal distribution, the non-parametric Friedman test will be used. For intergroup analyses, the parametric test, one-way ANOVA, will be used for those showing a normal distribution, and the non-parametric test, Kruskal Wallis H test, will be used for those not showing a normal distribution. Statistical significance will be accepted as $p < 0.05$ for all analyses.

Research

1. Güven SD, Çakırer Çalbayram N (2023). The effect of Helper skin tap technique on hepatitis B vaccine intramuscular injection pain in neonates: A randomized controlled trial. *Explore* 19(2): 238-242.

4. Türk Dil Kurumu (2023). Türk Dil Kurumu Sözlükleri [online]. Erişim adresi: <https://sozluk.gov.tr/>. [Erişim tarihi: 15.12.2023].

6. Cwynar CM Osborne K (2019). Immunization-Associated Pain: Taking Research to the Bedside. *Journal of Pediatric Health Care* 33(4): 446-454.

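### The between-group pain test names no time point, arm-versus-control contrast, baseline use or error rule, and the test behind N=72 is not stated

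*Combined protocol and SAP*

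**What the plan says.** The Data Analysis section has two separate steps, each with a normal and a non-normal branch.

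- Across time: "the parametric test ANOVA test will be used to compare repeated measurement results". When normality fails, the plan turns to another procedure: "If the values do not show a normal distribution, the non-parametric Friedman test will be used". Neither sentence mentions a group factor or a group-by-time term.
- Between groups: "For intergroup analyses, the parametric test, one-way ANOVA, will be used for those showing a normal distribution". Variables that fail normality go to Kruskal-Wallis instead.

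One threshold covers everything: "Statistical significance will be accepted as $p < 0.05$ for all analyses". No post-hoc test or adjustment is mentioned.

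The Video Camera paragraph has pain determined before, during and after vaccination. In substance, H1a sets vibration against routine vaccination, and H1b sets tapping against routine vaccination. The Aim places tapping before the injection and describes "the application of mechanical vibration to the injection site throughout the vaccination procedure on acute pain".

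Study Population and Sample uses effect size 0.31 from a cited thesis, alpha 0.05 and power 0.80. It adds that "the number of groups was taken as 3, and the number of measurements was taken as 3", and concludes: "The calculation resulted in a minimum participant number of 72". It does not state the test family, the effect-size definition or the correlation between measurements.

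**The concern.** Three gaps meet in one test.

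- **Question.** A three-arm omnibus test does not say which arm differs from control, and that is what H1a and H1b ask.
- **Time point.** Three pain scores exist and none is primary. The during and after scores may each be tested at 0.05, and nothing settles in advance which one decides the trial.
- **Sample size.** The calculation counts three measurements, but the between-group tests, read as single-time tests, use one. The stated 80% then cannot be tied to any between-group test that Data Analysis explicitly names.

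At stake is whether a significant result from 24 infants per arm can be read as confirming either main hypothesis, and whether the stated power describes the analysis that will be run.

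**Working it through.** **Inputs.** From Study Population and Sample: effect size 0.31, alpha 0.05, 3 groups, m=3 measurements, N=72 (24 per group). Assumed: 0.31 is Cohen's f, so f²=0.0961; correlation ρ=0.5, range 0.3 to 0.7. All power figures use the noncentral F distribution unless noted.

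**1. Reproducing 72.** For the between-groups test of a repeated-measures ANOVA, λ = f²·N·m/(1+(m−1)ρ), with df (2, N−3).
- N=72, ρ=0.5: λ = 0.0961×72×3/2 = 10.38, power 81.3%.
- N=69, ρ=0.5: λ = 9.95, power 79.4%. So 72 is the smallest balanced N.
- N=72 at ρ=0.3 and 0.7: 89.4% and 73.3%.

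At ρ=0.5 the other candidates need 21 (within-factor), 24 (interaction) and 105 (one-way ANOVA at one time). A different interaction parametrisation, λ = f²(N−3)(m−1), gives 69. Only the pooled between-groups test returns exactly 72.

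**2. Named tests, if f=0.31 holds at the tested time.** λ = f²N = 0.0961×72 = 6.92, df (2, 69): one-way ANOVA has 63.0%. For Kruskal-Wallis with relative efficiency 3/π = 0.955, λ = 6.61 and power is 60.8%.

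**3. Named tests, if 0.31 is the three-time average.** Randomisation implies no difference before the procedure. If the effect is shared equally by the during and after scores, each has f = 0.31×3/2 = 0.465. Then λ = 0.465²×72 = 15.57, and one-way ANOVA has 94.3%. For Kruskal-Wallis, λ = 14.87 and power is 93.2%.

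Conversely, if 0.31 is a single-time effect present at two of three times, the pooled test in step 1 sees f = 0.31×2/3 = 0.207. At ρ=0.5, λ = 4.61 and power is 45%. If it is present at one of three times, power is 14%.

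**4. Error over time points.** Two tests at 0.05 give a false-positive rate of at most 0.10, or 1−0.95² = 0.0975 if independent. In simulated 0-7 scores (assumed infant and residual SD 1.2, 24 per arm, 4,000 trials, three assumed mean profiles), testing during and after gave 8-9%. Counting the pre-procedure test as well gave 12-14%.

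**5. Baseline-adjusted analysis, f=0.31 at the primary time.** For the omnibus ANCOVA, λ = f²N/(1−ρ²), df (2, 68), with ρ now the correlation with the pre-procedure score. The unadjusted test has 63.0%.

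| ρ | Omnibus ANCOVA | Holm contrast, both arms work | Holm contrast, one arm works |
|---|---|---|---|
| 0.1 | 63.4% | – | – |
| 0.3 | 67.3% | 58% | 54% |
| 0.5 | 76.2% | 68% | 63% |
| 0.7 | 90.7% | 86% | 81% |

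The contrasts are simulated on normal data (20,000 runs). When two groups share a mean, f=0.31 is a difference of 0.31×3/√2 = 0.66 SD. Familywise error under the null was 4.7-4.9%.

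**The case against.** **The repeated-measurement ANOVA could be a mixed model.** The sample-size inputs follow the type of test, with three groups and three measurements. A mixed ANOVA with group as the between-infant factor is therefore a possible reading of the normal branch, and its between-groups test is the one that reproduces 72. A reader might infer that the plan contains no joint test at all; the text does not support that. However, it does not name the group factor, and it assigns group comparison to other tests. In the non-normal branch Friedman has no group factor. A 0-7 integer score could well fall in that branch.

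**The trial may not be underpowered.** A reader might infer from 61-63% that N=72 is too small. That holds only if 0.31 is the effect at the single time tested. If it is the three-time average described in step 3, power is about 93-94%. The documents support neither reading over the other. This objection stands, and no single figure can replace 0.80.

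**The contrast gap is small.** H1a and H1b are worded as control against the study groups, so an omnibus step is not foreign to them. With three groups, pairwise tests run only after a significant omnibus test also control the error: 40,000 simulated normal trials gave 4.1% under the null, and 4.7% for the inactive arm when one arm works. So Holm is one option. The contrasts still have to be written down, and gating does nothing about the choice of time point.

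**Baseline adjustment may gain little.** At a baseline correlation of 0.1 the gain is 0.4 percentage points. The documents give no correlation, and pre-procedure scores may sit near zero.

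**Conclusion.** The concern holds as a gap in specification. The missing time point, contrasts, baseline use and error rule can be read directly from Data Analysis in both branches and depend on no assumption. Followed as written, the plan does not answer H1a or H1b, and it allows a false-positive rate above 5% across the during and after scores (8-9% under the assumed score distributions, at most 10%).

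The sample-size part holds in a limited form: the test family, effect-size definition and correlation are not stated, so the 80% cannot be attached to a named between-group test. It does not follow that power is inadequate. The named single-time tests range from about 61% to 94% according to what 0.31 means. Nor does the absence of a primary time point imply any intention to report selectively.

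The reproduction of 72 rests on reading 0.31 as Cohen's f and on a correlation of 0.5. The simulated figures rest on means and SDs that the documents do not give.

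**What to change.** Before data are seen, in Data Analysis:

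1. Name one primary post-baseline NIPS comparison. The score during vaccination is reasonable given when the interventions are applied; the during/after average is an acceptable alternative. Make the other time points and outcomes secondary.
2. Analyse it by ANCOVA with group and pre-procedure NIPS and robust standard errors, with Kruskal-Wallis as a sensitivity analysis.
3. Pre-specify vibration versus control and tapping versus control, holding familywise error at two-sided 0.05 by Holm or by pairwise tests gated on the three-group omnibus test.
4. Label Friedman and other within-arm time tests descriptive.

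In Study Population and Sample, state the test family, the effect-size definition and the assumed correlation. Give the power of N=72 for the named analysis as a range over those assumptions, not as a single 0.80. The Holm columns in step 5 are one end of that range, since they take f=0.31 at the primary time.

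**Cost.** Wording only, because pain is already to be scored at all three times. If 80% per contrast is wanted with f=0.31 at the primary time and both arms working, N becomes about 111, 93 or 63 at correlation 0.3, 0.5 or 0.7 (123, 105 or 72 if one arm works).

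**Downsides.** A linear model is applied to a bounded 0-7 score, the stated power may look less favourable, and adjustment gains little if the baseline correlation is low. The choice of primary measure also matters. For a simulated 1-point benefit, the during score has about 50% power per contrast. The during/after average has 69-73% if the benefit lasts and 20-21% if it does not.

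### Crying time and four vital signs are judged at p<0.05 with no ordering or error control: about a 30% chance of a false non-pain effect over seven independent post-start tests, about 15% to 27% if they are correlated

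*Combined protocol and SAP*

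**What the plan says.** All references are to the combined protocol and SAP.

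- **Data Analysis** gives the significance rule: "Statistical significance will be accepted as $p < 0.05$ for all analyses". On the tests between arms it says: "For intergroup analyses, the parametric test, one-way ANOVA, will be used for those showing a normal distribution". Otherwise a rank-based alternative, Kruskal-Wallis, applies. The section does not limit these tests to particular outcomes or time points.
- **Aim** says that the study looks at the effect of tapping and vibration "on acute pain, crying duration, and physiological parameters that may occur due to intramuscular injection".
- **Main Hypotheses** has two pairs of hypotheses, one for vibration and one for tapping. Both concern pain only. No hypothesis names crying or a vital sign.
- **Newborn Baby Observation Form** lists the non-pain values. Crying gives a single value: "crying time with the start of the vaccination procedure". Temperature and breathing rate are each read twice, once on either side of the vaccination. The remaining two vital signs are each read three times: "oxygen saturation and heart rate before, during, and after the procedure".

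The plan does not rank the non-pain outcomes, name one reading for each, or adjust for multiple tests.

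**The concern.** The plan is not silent on the threshold. It states a rule, and that rule gives every non-pain comparison the same standing as the pain comparison. The Aim names these outcomes as things that the study investigates, so a significant result on any one of them can be reported as a finding on crying or physiology.

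If neither technique changes any of these outcomes, several unadjusted tests will still often produce one significant result. A report that followed the plan exactly could then present it as a benefit, even where the pain comparison was negative.

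**Working it through.** **1. The plan's own figure.** Study Population and Sample gives effect size 0.31, error 0.05, power 0.80, three groups and three measurements, with a result of 72 (24 per group). I read 0.31 as Cohen's f and used the between-groups test of a repeated-measures ANOVA. The correlation among measurements is not stated; I assumed 0.5.

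- λ = f² × N × m / (1 + (m − 1)ρ) = 0.0961 × 72 × 3 / (1 + 2 × 0.5) = 20.76 / 2 = 10.38, with 2 and 69 degrees of freedom.
- Power is 0.813, and 72 is the smallest multiple of three that reaches 0.80.

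So 72 reproduces. Only the 24 per arm is used below.

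**2. Count of non-pain values** (Newborn Baby Observation Form).

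| Outcome | Before | During or after |
|---|---|---|
| Crying time | 0 | 1 |
| Temperature | 1 | 1 |
| Respiratory rate | 1 | 1 |
| Oxygen saturation | 1 | 2 |
| Heart rate | 1 | 2 |
| Total | 4 | 7 |

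Only the seven values in the right-hand column can show an effect of vibration or tapping.

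**3. Independent tests.** With k tests at 0.05 and no true effect, the chance of at least one significant result is 1 − 0.95^k.

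- k = 7: 1 − 0.698 = 30.2%.
- k = 5 (one per outcome): 1 − 0.774 = 22.6%.

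**4. Correlated tests.** Values from the same infant are likely to be correlated, and the documents give no figure. I simulated three arms of 24 with normal outcomes, no effect, and one-way ANOVA at 0.05 on each of the seven values (20,000 trials per setting, simulation error about 0.3 percentage points).

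| Assumed common correlation | At least one of 7 significant |
|---|---|
| 0.3 | 27.4% |
| 0.5 | 23.4% |
| 0.7 | 18.9% |
| 0.8 | 15.5% |

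**5. Price of a strict rule.** Holm over five tests starts at 0.05 / 5 = 0.01. For one omnibus test at f = 0.31 and N = 72, λ = 0.0961 × 72 = 6.92 with 2 and 69 degrees of freedom. Power is 0.630 at 0.05 and 0.379 at 0.01. The value of f is borrowed from the pain calculation as an illustration.

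**The case against.** **The count is an assumption.** The plan does not say at which time points the arms are compared, or that each reading is tested separately. This stands: seven is a reading of open wording. The narrower reading, one test per outcome, still gives about 23% if the tests are independent. Tests within arms over time and any pairwise follow-ups also fall under the same threshold and are not counted here.

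**Independence is the least plausible case.** This also stands, and it is why 30% is given with the 15% to 27% range. The correlations are mine.

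**The pain-only Main Hypotheses already imply an order.** They do, in part, and this makes the point one about secondary claims. But Data Analysis does not carry that order into its threshold, and the Aim lists the outcomes together.

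**A larger figure is tempting.** A reader might count all 11 readings and infer a 43% chance (1 − 0.95^11 = 43.1%). The documents do not support that as a chance of a false effect. Four of the 11 are taken before the procedure, and a chance difference there is baseline imbalance, not an apparent benefit.

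**Correction across secondary outcomes is a matter of preference.** Largely fair. Clear labelling, with estimates and intervals, removes most of the harm, and the loss of power under Holm is real. Holm is therefore needed only if a non-pain effect is to be claimed as established.

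**Conclusion.** The concern holds for claims about crying and vital signs. The inflation is three to six times the nominal 5% (15.5 / 5 = 3.1; 30.2 / 5 = 6.0). This rests on three arms of 24, seven post-start values each tested between arms by one-way ANOVA at 0.05, no true effect, and common correlations from 0 to 0.8.

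A reader might infer that the pain result or the sample size is compromised. Neither is. The tests of the pain hypotheses do not depend on the non-pain tests, and 72 reproduces. Whether the two pain comparisons need their own adjustment is a separate matter. The text should be changed before analysis, but this is a weakness in the interpretation of secondary results and not a flaw in the main comparison.

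**What to change.** In Data Analysis, replace the clause that extends the threshold to every analysis with wording to this effect:

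1. The p<0.05 rule applies to the pain hypotheses.
2. Crying time, heart rate, oxygen saturation, temperature and respiratory rate are supportive outcomes. One post-start value is named for each before the data are seen. Only heart rate and saturation need a choice, between the reading during the procedure and the one after it.
3. Each is reported as the difference of each technique from control, with a 95% confidence interval labelled as unadjusted. The other readings are descriptive.
4. No effect on a non-pain outcome is claimed as established on an unadjusted p<0.05. If the sponsor wants such a claim, it must pass Holm over the five tests, which holds the familywise chance to at most 5%. An omnibus test does not show which technique differs from control, so a claim for one technique also needs a stated follow-up comparison.

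**Cost.** Wording only, with no added infants, visits or measurements. The non-pain results become supportive, or else face a stricter threshold: omnibus power at f = 0.31 falls from 0.63 to 0.38 at the first Holm step. The plan states no power for these outcomes, so no stated power is lost.
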